Title: PHASE II RANDOMIZED PLACEBO-CONTROLLED CLINICAL TRIAL OF GENISTEIN IN REDUCING THE TOXICITY AND IMPROVING THE EFFICACY OF INTRAVESICAL THERAPY

Study Principal Investigator: [name] MD

Study Sponsor: [name]

Study Co-Principal Investigator: [name] PhD

Study Supporter: DSM Nutritional Products

Version Date: 16 Jul 2019

Schema:

E n r o ll m e n t	44 TaT1 Tis superficial bladder cancer patients scheduled to receive BCG intravesical therapy will be consented Estimated Timeline: until 44 subjects are enrolled (approximately 2 years)	R a n d o m iz a ti o n	Arm 1: BCG intravesical therapy with placebo pills for 10 weeks (22 subjects) Arm 2: BCG intravesical therapy with 30 mg genistein supplement PO TID for 10 weeks (22 subjects)	F o ll o w - u p	Arm 1: Followed-up according to standard after-treatment care: one-month post-treatment appointment and subsequent doctor visits. Arm 2: Followed-up according to standard after-treatment care: one-month post-treatment appointment and subsequent doctor visits.
--	---	---	--	---------------------------------------	--

Patients will take either 30 mg tablets of placebo or genistein supplement PO TID, for 6 weeks during BCG intravesical therapy and will continue for 4 weeks following therapy.

1. Abstract:

Patients who are treated with BCG intravesical therapy for TaT1 Tis superficial bladder cancer often develop adverse effects (urinary tract symptoms) which limit the dose (and therefore the efficacy) of therapy and result in poor quality of life. Genistein is a nutritional supplement with anti-inflammatory properties which might help alleviate adverse effects of intravesical therapy that are due to inflammation. Additionally, genistein also has anti-tumor and immunopotentiating properties and has been shown to have no known side effects. Our hypothesis is that genistein given together with BCG intravesical therapy will reduce its adverse effects and improve the efficacy of therapy. Patients (N=44) scheduled for intravesical therapy will be randomly assigned to take 30 mg tablets of genistein supplement (N=22) or placebo (N=22) PO TID during therapy and one month post therapy.

2. Introduction and Background:

BCG intravesical therapy is a form of immunotherapy commonly used to prevent the recurrence of noninvasive bladder cancer, which occurs in approximately 50-80% of bladder cancer patients within 5 years. 10-20% of all superficial bladder cancer patients will progress beyond superficial recurrence within 5 years. Smoking, poor diets, and large body weights are all potential risk factors for recurrence, but there is also a high propensity for bladder cancer recurrence in general due to its aggressive nature. As treatment, BCG intravesical therapy is instilled in the bladder using a urinary catheter. The intravesical therapy remains in the bladder for about two hours until the patient urinates. The treatment is usually once a week for six weeks and then repeated every 3-6 months for two years. However, intravesical therapy typically causes urinary tract symptoms, such as pain, frequency, burning, inflammation, and bleeding in patients. Symptoms may occur after the very first treatment or become worse over time as therapy continues. As a result, the dose of therapy is often reduced so that symptoms can be treated symptomatically with antibiotics or pain medication. Dose reduction is generally done in 50% increments, and the decision to reduce the treatment dosage is often subjective based on each patient's perception of symptoms.

The isoflavone genistein (4,7,4'-trihydroxyisoflavone) is a phytoestrogen found in high levels in soy products and can be taken as a nutritional supplement for its antioxidant benefits and its estrogenic properties. The genistein supplement is sold over the counter and has less soy isoflavone than commonly found in many healthy diets. For comparison, an 8 ounce glass of soy milk has 15 mg of genistein. Studies have used up to 300 mg of genistein supplement daily, and it has been shown as safe, well accepted, and well tolerated with no known significant toxicities.

Recent epidemiologic reports show that some Asian countries with high soy consumption have a smaller incidence of prostate carcinoma and studies suggest it might be due to the anticancer effects of soy. A study of 41 subjects in 2003 showed that there was a significant slow in the rate of PSA rise in prostate cancer patients after taking 100 mg of genistein supplement daily for 6 monthsⁱ A recent study of 52 subjects in 2010 showed that the short-

term, neoadjuvant synthetic aglycone genistein supplement was comparable to high soybean consumption and indicated a possible therapeutic benefit in early CaP, a borderline significant serum PSA reduction, and normalization of PSA in malignant prostate tumors.ⁱⁱ Genistein has been reported to have both anticancer and anti-inflammatory effects that may inhibit prostate cancer cell growth and metastasis, as well as an effect on decreased incidence of urinary, gastrointestinal, and erectile dysfunctions when 42 patients were given 100 mg genistein supplement daily for 6 months in conjunction to radiation.ⁱⁱⁱ Additionally, a small pilot study of 8 children receiving chemotherapy and/or radiation were given 8 mg of the genistein supplement daily and findings suggest that the genistein supplement reduced the adverse effects of treatment while causing no side effects.^{iv} The results from these studies suggest that further clinical investigation should be warranted to apply soy phytochemicals, as a potential prevention regimen for cancer progression .

In a large prospective cohort of 2000 Chinese men, the association between dietary isoflavone and lower urinary tract symptoms (LUTS) were studied using standardized structured questionnaires. A total of 96.2 % of subjects reported some consumption of genistein, glycinein, or daidzein. In ordinal multinominal logistic regression, subjects with dietary total isoflavone of more than 5.1 mg were significantly less likely to suffer from more severe LUTS.^v The aforementioned studies suggest that the use of genistein in combination with intravesical therapy will allow for more effective treatment of bladder cancer.

3. Investigational Product Information:

This study will use the synthetic non-soy genistein supplement, Bonistein™ . Bonistein™ has been compounded into tablets named I-Cool ®. Each I-Cool tablet contains 30 mg of genistein (Bonistein™). I-Cool ® and the corresponding placebo tablets are supplied by DSM Nutritional Products. DSM Nutritional Products as the study product supplier, provides Certificate of Analysis to Study Sponsor. Patients enrolled in the study will be receiving I-Cool ® tablets or the corresponding placebo tablets.

4. Objectives:

4.1 Primary objective

The primary study endpoint is the change in severity of urinary symptoms over time as determined by the IPSS questionnaire score, specifically comparing the symptoms at the 1st BCG treatment (baseline) to the symptoms at the 6th week of treatment. The difference in the degree of urinary symptoms between the placebo and genistein supplement arms will help reflect whether genistein supplement can improve the quality of life in BCG intravesical therapy patients.

4.2 Secondary objective

- a) A secondary study endpoint will be the presence of cancer and the rate of recurrence as determined by the 10-week biopsy or subsequent standard follow-up visits.
- b) A second secondary study endpoint will be the total dose of intravesical therapy administered over the 6 weeks of treatment. If subjects develop fewer urinary tract symptoms as a result of the genistein supplement, then hypothetically, intravesical therapy dosing would not have to be reduced as much. This will be measured by looking at the level of dose reduction for each treatment week and comparing it across the two arms.

5. Study Design and Methods:

At the pre-operative office visit before intravesical therapy, eligible patients will be screened and enrolled into the study by going through the consent process and signing the consent and HIPAA forms. Each patient will need to report all other medications so that the study team can assess whether certain medications might affect trial outcome.

Patients will be randomized into Arm 1 (placebo) or Arm 2 (genistein supplement) at a ratio of 1:1 stratified by one dichotomized prognostic factor, age. The dichotomization will take place based on whether they are age 60 and above or whether they are age 59 and below. This will allow for similar age groups to be placed in each arm, so that the degree of urinary symptoms while receiving treatment is not skewed depending on the patient's age.

Patients are treated with intravesical therapy once a week for 6 weeks and then return to the office approximately four weeks later for a post-operative visit and biopsy, as is standard care. Study subjects will take their genistein or placebo tablets for a total of 10 weeks, which includes the length of their treatment, as well as the 4 weeks before the post-op visit. Each patient will fill out an International Prostate Symptom Score (IPSS) questionnaire at their baseline office visit when consented. Patients will fill out an IPSS questionnaire at each subsequent intravesical therapy session and their final one-month follow-up appointment (at 10 weeks) either in person or via phone call with a study team member. The IPSS questionnaire will gauge their urinary symptoms throughout their therapy and provide measurable symptom scores for the two arms. The biopsy at 10 weeks, as well as standard 3 months follow-up appointments, is standard care for superficial bladder patients and will help determine cancer rate of recurrence.

	Baseline	BCG Week 1-6 ^b	10 Week ^c
Placebo Arm	
 • Screening (Physical Exam,^a Vitals,^a complete blood count and serum chemistry analyses, ^a Urine Dipstick, IPSS Questionnaire) • Enrollment • Randomization 	
 • Urine Dipstick, Interval History, Vitals, IPSS Questionnaire* • BCG Intravesical Therapy • 6 weeks of placebo (30 mg, PO TID) • Continue taking placebo for remaining 4 weeks before biopsy 	
 • Bladder Cystoscopy (Biopsy recommended, but not mandatory) • Urinary cytology (if indicated) • Interval History • IPSS Questionnaire* • Physical Exam • Vital signs • Complete blood count and serum chemistry panel is recommended, but not mandatory
Genistein Supplement Arm	
 • Screening (Physical Exam, ^a Vitals,^a complete blood count and serum chemistry analyses, ^a Urine Dipstick, IPSS Questionnaire) , • Enrollment, • Randomization 	
 • Urine Dipstick, Interval History, Vitals, IPSS Questionnaire*, • BCG Intravesical Therapy • 6 weeks of genistein Supplement (30 mg, PO TID) • Continue taking genistein Supplement for remaining 4 weeks before biopsy 	
 • Bladder Biopsy (pathology) • Urinary cytology • Interval History • IPSS Questionnaire* • Physical Exam • Vital signs • Complete blood count and serum chemistry panel is recommended, but not mandatory

^a Within 2 months before the first dose of study treatment.

^b A range of 7 days before or after the scheduled visit is allowed or per standard of care. If BCG treatment is interrupted or discontinued Urine Dipstick, Interval History, and Vitals may not be collected per standard of care.

^c A range of 2-3 weeks before or after the 10 week is allowed or per standard of care.

*IPSS Questionnaire may be collected via phone call.

6. Participant Selection:

44 patients will be enrolled in the trial, with 22 subjects on each arm. Potential subjects will be superficial bladder cancer patients in the Department of Urology who are scheduled for their standard-of-care BCG intravesical therapy.

Inclusion Criteria:

1. Male or female gender
2. 18 years or older
3. Diagnosis of superficial bladder cancer
4. Scheduled for induction BCG intravesical therapy
5. Willing and able to give blood sample
6. Willing and able to fill out a pill diary to ensure compliance
7. Willing and able to sign informed consent

***Birth Control is not required for this study!

Exclusion Criteria:

1. Patients who are pregnant
2. Diagnosis of muscle-invasive bladder cancer
3. Unwillingness to follow study protocol and compliance procedures
4. HIV positive or immunocompromised
5. Receiving concurrent immunotherapy or chemotherapy
6. Presence of concurrent second cancer (active, not history)

7. Quality of Life:

This study follows standard of care for all superficial bladder cancer subjects. All subjects will receive standard BCG intravesical therapy for six weeks and return for a one-month post-operative visit and biopsy. Both the control and intervention arms will receive the same care, other than taking the genistein supplement or placebo. While genistein supplement is not a standard part of treatment, it has been shown to not have any significant toxicities. It is expected that the subjects taking genistein supplement will have a better quality of life due to a possible reduction in urinary symptoms, such as hematuria, infection, frequency, urgency, and retention, when compared to those subjects receiving standard treatment without the genistein supplement. Each patient's perception of quality of life will be seen indirectly throughout the BCG treatment, as it is a supplemental question on the IPSS Questionnaire.

Quality of life will be assessed for both arms during an interim analysis and stopping criteria will be determined on the degree of individual AEs as well as an interim analysis of both arms. Subjects with toxicities of Grade 3 or higher according the NCI CTCAE Version 4.0 will be immediately discontinued from the study pill. Additionally, the interim analysis will take place after 22 patients (11 on each arm) have been enrolled, treated, and biopsied. If the genistein supplement arm has statistically significant toxicities reported or greater degree of bladder cancer biopsies then we will immediately discontinue any future study enrollment. If the genistein supplement arm has significant Grade 3 toxicities, we will reduce the genistein supplement given by 1 tablet for 10 more patients, and if the toxicities persist after that, the study will be stopped.

8. Statistical Consideration:

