8.2.2 Secondary analysis

- a) For the secondary end point of recurrence rate defined by 10-week biopsy, the Chi-squares test is used to test the rate difference between the two arms, and a logistic regression is needed to further adjust potential covariates, e.g. total BCG therapy dose.
- b) For the secondary end point of the total dose of intravesical therapy administered over 6 weeks, we consider the two-sample t test and/or sum rank test to test the difference between two arms. If genistein supplement works by reducing symptoms and maintaining the therapy dose, we expect to see a higher total therapy dose in its arm than in the placebo arm.
- c) We will also explore the change of IPSS score over time by the GEE model in which the repeated measurements of IPSS score are treated as outcome. Treatment, time, interaction between treatment and time, and intravesical therapy dose enter the model as predictors and time-dependent covariate.

9. Adverse Event Reporting:

According to 21 CFR 312.32, *Adverse event* means any untoward medical occurrence associated with the use of a drug in humans, whether or not considered drug related. A *Serious adverse event* or *serious suspected adverse reaction* is an adverse event or suspected adverse reaction is considered "serious" if, in the view of either the

investigator or sponsor, it results in any of the following outcomes: Death, a life-threatening adverse event, inpatient hospitalization or prolongation of existing hospitalization, a persistent or significant incapacity or substantial disruption of the ability to conduct normal life functions, or a congenital anomaly/birth defect. Important medical events that may not result in death, be life-threatening, or require hospitalization may be considered serious when, based upon appropriate medical judgment, they may jeopardize the patient or subject and may require medical or surgical intervention to prevent one of the outcomes listed in this definition. Examples of such medical events include allergic bronchospasm requiring intensive treatment in an emergency room or at home, blood dyscrasias or convulsions that do not result in inpatient hospitalization, or the development of drug dependency or drug abuse.

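### The 10-week schedule makes biopsy optional for placebo but not for genistein, so ascertainment of recurrence could depend on arm

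*Combined protocol and SAP*

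**What the plan says.** The schedule table in Section 5 has one row per arm. In the 10-week column:

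| 10-week item | Placebo row | Genistein row |
|---|---|---|
| Bladder assessment | "Bladder Cystoscopy (Biopsy recommended, but not mandatory" | "Bladder Biopsy (pathology" |
| Cytology | "Urinary cytology (if indicated" | Listed without a condition |
| Interval history, IPSS, physical exam, vital signs, blood tests | Same in both rows | Same in both rows |

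Footnote c, the only footnote on this column, deals with the visit window and applies to both rows.

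The text does not separate the arms. Section 5 says that patients "return to the office approximately four weeks later for a post-operative visit and biopsy, as is standard care". Section 7 also has all subjects return for a biopsy and adds: "Both the control and intervention arms will receive the same care, other than taking the genistein supplement or placebo".

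The endpoint and the interim look both depend on this assessment. Section 4.2(a) takes "the presence of cancer and the rate of recurrence as determined by the 10-week biopsy or subsequent standard follow-up visits". Section 8.2.2(a) is narrower: "For the secondary end point of recurrence rate defined by 10-week biopsy, the Chi-squares test is used". Section 7 states that "the interim analysis will take place after 22 patients (11 on each arm) have been enrolled, treated, and biopsied", and Sections 7 and 10 halt enrollment if biopsies show more bladder cancer in the genistein arm.

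**The concern.** The table cannot be reconciled with the text of Sections 5 and 7. If the table governs, the chance of finding cancer at week 10 depends on the assigned arm, and a comparison of recurrence no longer compares like with like.

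The direction of the error is open, because Section 8.2.2(a) does not say what happens to a patient without a biopsy:

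- **Unbiopsied placebo patients count as negative.** Placebo disease is missed and genistein looks worse.
- **Only biopsied patients count, and placebo biopsies are partly for cause.** The placebo rate is inflated and genistein looks better.
- **Only biopsied patients count, and placebo biopsies are unselected.** There is no bias, only fewer placebo patients.

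Recurrence is the trial's only cancer outcome. An apparent excess in the genistein arm could also stop enrollment at the interim look.

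**Working it through.** **The plan's own figure.** The documents give no sample size, power or expected rate for recurrence. The only power figure is 83% for the IPSS endpoint in Section 8.1. It reproduces: a noncentral t calculation with difference 3, SD 3.5, one-sided 0.05 and n = 20 × 0.955 = 19.1 per arm gives 83.0%. That figure does not involve biopsy. Only its 20 patients per arm is used below.

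**Is it a PDF-reading artefact?** Unlikely. Both cells are complete, and the other five 10-week items match. The blood tests are marked as optional in both rows, whereas biopsy is marked as optional in one.

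**Illustration; every rate is an assumption.** The true 10-week disease rate is p in both arms. All genistein patients are biopsied. A fraction f of placebo patients is biopsied, and the share of placebo disease found is f + (1 − f)/2.

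For p = 0.30 and f = 0.5:

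- Share found = 0.5 + 0.25 = 0.75.
- Expected placebo positives = 20 × 0.30 × 0.75 = 4.5.
- Placebo rate with all patients as denominator = 4.5/20 = 22.5%.
- Placebo rate with biopsied patients only = 4.5/10 = 45%.
- Genistein rate = 30% throughout.

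Exact binomial enumeration of the uncorrected two-sided 5% chi-square test gives:

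| Handling | Genistein vs placebo | n | Probability of a false result |
|---|---|---|---|
| Equal ascertainment | 30% vs 30% | 20 vs 20 | 2.7% worse, 2.7% better |
| Unbiopsied count as negative | 30% vs 22.5% | 20 vs 20 | 7.9% worse |
| Biopsied only, partly for cause | 30% vs 45% | 20 vs 10 | 13.5% better |
| Biopsied only, unselected | 30% vs 30% | 20 vs 10 | 2.9% better |

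Over p = 0.2, 0.3 and 0.4 and f = 0.5 and 0.75, the false-worse probability under the second rule runs from 3.9% to 9.9%. The false-better probability under the third rule runs from 5.0% to 18.3%. The equal-ascertainment reference stays between 2.4% and 2.7%.

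**Check under different assumptions, p = 0.30.**

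- Unbiopsied placebo patients are classified by cystoscopy with sensitivity s, and a fraction b is biopsied. The observed rate is p[b + (1 − b)s]. With s = 0.6 and b = 0 it is 18%; with s = 0.8 and b = 0.5 it is 27%. Genistein looks worse.
- Only biopsied patients are analysed, with biopsy in 90% of those with cancer and 20–50% of those without. The observed rate is 0.27/(0.27 + 0.35) = 44% up to 0.27/(0.27 + 0.14) = 66%. Genistein looks better.
- Biopsy is done in 70% regardless of disease. The observed rate is 30%, with 14 of 20 placebo patients contributing.

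**Interim timing, a side point.** Read literally, 11 biopsied placebo patients need 11/f placebo patients: 22 at f = 0.5, 14.7 at 0.75 and 12.2 at 0.9. At f = 0.5, the chance that all 22 placebo patients yield fewer than 11 biopsies is 1 − 0.584 = 42%. Section 10 instead sets the look at half of accrual.

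**The case against.** The strongest objection is that staff could not follow the table by arm. The trial is placebo-controlled with matching tablets, and a urologist who does not know the allocation cannot order biopsy differently. The text also points to equal care, so one cell was probably edited and the other not. This is fair, and it is why the bias is only conditional. But the documents do not say who is blinded. If staff are blinded, the schedule cannot be carried out as written; if they follow it, it discloses the allocation. It needs correcting either way.

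The second objection is to the size. No input comes from the documents, and the absence of a qualifier in the genistein row does not establish that every patient there is biopsied. At 90% placebo uptake and p = 0.30, the false-worse and false-better probabilities are 3.4% and 3.3%, close to the 2.7% reference. Section 8.2.2(a) does not specify an uncorrected test. With continuity correction, 7.9% and 13.5% become 3.8% and 7.5%; with Fisher's exact test they become 4.2% and 9.8%. All of this stands. The reference falls too: the same enumeration with equal ascertainment gives 1.1% each way with the correction and 1.2% with Fisher's test. The distortion relative to equal arms therefore remains.

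The third objection is that the missing-biopsy rule and the interim trigger would be open even with matching cells. That is true of both. The missing rule belongs here because it decides the direction of the bias. The interim timing carries no weight in the conclusion.

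**Conclusion.** The concern holds. The inconsistency between the two table cells, and between the table and Sections 5 and 7, is certain from the text. It looks like a drafting inconsistency rather than a deliberate choice, though that is inference.

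The bias is possible, not established. It requires that the table be followed by arm, and its sign depends on a rule the plan does not give. Under the assumed rates its size ranges from negligible, at high placebo uptake or with unselected biopsies analysed alone, to an 18.3% chance of a false significant benefit.

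The endpoint is secondary and unpowered, and the primary IPSS analysis and its 83% power are untouched. The point should be corrected, but it does not threaten the trial's main question. The reason to act is that a cancer comparison and a stopping rule both rest on this assessment.

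**What to change.** 1. Make the two 10-week cells identical, for both biopsy and cytology, using whichever standard-care assessment the sponsor intends.
2. In Sections 4.2(a) and 8.2.2(a), define recurrence from that common assessment. Give one rule for patients without a biopsy, applied the same way in both arms, and state the denominator.
3. Use the same definition and denominator for the interim stopping rule in Sections 7 and 10.
4. Report the number biopsied in each arm.
5. If biopsy stays optional, trigger the interim look on patients who have completed the 10-week assessment rather than on patients biopsied.

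The cost is a table correction and one or two sentences in Sections 8.2.2(a) and 7, with Section 4.2(a) aligned to them. It adds no procedure beyond what Sections 5 and 7 already describe as standard care. If optional biopsy is chosen for both arms, the biopsy-based definition in Section 8.2.2(a) and the biopsy statements in Sections 5 and 7 must change as well.

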Adverse events will be recorded at each study visit via direct patient communication as well as through patient questionnaires. The severity of the AEs will be graded according to NCI CTCAE Version 4.0. Subjects with toxicities of Grade 3 or higher will be immediately discontinued from the study pill for the remainder of treatment. Any BCG intravesical therapy modifications will be done according to doctor analysis with an effort on alleviating toxicities as needed. In order to be evaluable, patients will need to receive at least three BCG instillations. If BCG treatment is interrupted or discontinued, only IPSS scores will be obtained via phone call. If a SAE occurs, we will promptly report it to our IRB upon discovery and follow the subject until the SAE is resolved. Adverse events will be reported to the IRB according to their requirements.

IND safety reports will be sent to the FDA in accordance with 312.32 the FDA's *Guidance for Industry and Investigators: Safety Reporting Requirements for INDs and BA/BE studies*. IND safety reports will document any aggregate adverse events, adverse reactions suspected adverse reactions, or serious adverse events. If the event is considered to be unexpected fatal or life-threatening, the IND safety report will be sent as soon as possible and within 7 business days of the investigator being notified. If necessary, the investigator will report any serious or life-threatening event initially by facsimile or telephone prior to formal submission. IND safety reports will also be submitted to the FDA if any related safety information is released from other sources. Any nonserious adverse events will be reported to the FDA in aggregate on an annual basis.

10. Data and Safety Monitoring Plan (DSMP):

Once the study has reached 50% accrual, investigators will plan to initially evaluate the results. A group of physicians from the Winship Cancer Institute at Emory University will review the data and questionnaires to see how patients are reacting to the genistein supplement arm or whether there are drug compliance issues, such as failure to take the pills per protocol. If the genistein supplement arm has statistically significant toxicities reported or greater degree of bladder cancer biopsies then we will immediately

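### Sections 7 and 10 set different triggers for the same interim look, and the Section 7 trigger, read literally, depends on a biopsy that the schedule makes optional in the placebo arm only

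*Combined protocol and SAP*

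**What the plan says.** **Trigger in Section 7 (Quality of Life).** "the interim analysis will take place after 22 patients (11 on each arm) have been enrolled, treated, and biopsied".

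**Trigger in Section 10 (Data and Safety Monitoring Plan).** "Once the study has reached 50% accrual, investigators will plan to initially evaluate the results". No treatment, follow-up or biopsy condition is attached.

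Both sections then give the same stopping rules. Enrolment stops if the genistein arm shows statistically significant toxicity or a worse biopsy result, and a further rule covers Grade 3 toxicity. The two sections therefore describe one look, not two.

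**Biopsy status.** In the Section 5 schedule, the 10-week column for the placebo arm reads "Bladder Cystoscopy (Biopsy recommended, but not mandatory". The same column for the genistein arm reads "Bladder Biopsy (pathology", with no optional wording. The text of Section 5 says "The biopsy at 10 weeks, as well as standard 3 months follow-up appointments, is standard care for superficial bladder patients". Section 7 says "All subjects will receive standard BCG intravesical therapy for six weeks and return for a one-month post-operative visit and biopsy", and adds that care is the same in both arms apart from the study tablets.

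**Timing.** The Schema expects accrual to run "until 44 subjects are enrolled (approximately 2 years"). The schedule footnote for the 10-week visit says "A range of 2-3 weeks before or after the 10 week is allowed or per standard of care".

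**The concern.** The look decides whether enrolment continues, so its timing fixes which data that decision uses and how many patients are still to be enrolled. With two triggers, two people following the protocol could hold the look at different times on different data.

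Under Section 10, the most recently enrolled patients have not reached week 10, so the biopsy comparison is incomplete. Under Section 7 read literally, the look waits for 11 placebo patients to have a procedure that the schedule does not require of them. I found no fallback if 11 is not reached, and no pause in enrolment before the look.

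**Working it through.** **Inputs from the documents**
- Total 44, 22 per arm, 1:1 (Schema; Section 6).
- Accrual in about 2 years (Schema).
- Biopsy visit at 10 weeks, up to 3 weeks either side, so 7 to 13 weeks (Section 5).
- Drop-out or non-compliance 10% (Section 8.1).

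**Assumptions**
- Uniform accrual, 44 / 2 = 22 patients a year, with half of those enrolled on placebo at any time.
- Placebo biopsy uptake *u*. The documents give no figure, so a range is shown.
- Lag counted from enrolment. Expected values only, except where a probability is given.

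**Step 1. The plan's own count.** 50% of 44 = 22 = 2 x 11. The two sections agree on the number of patients but not on what must have happened to them.

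**Step 2. Gap with every biopsy done.** Enrolment during 10 weeks = 22 x 10/52 = 4.2 patients.
- At 50% accrual, patients with 10-week data: 22 - 4.2 = 17.8, about 18.
- When the 22nd patient reaches week 10: 22 + 4.2 = 26.2, about 26 enrolled.

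**Step 3. Literal Section 7 trigger, no drop-out.** Placebo patients needed = 11/*u*. Total enrolled by then = 22/*u*. Adding the 10-week wait, enrolled at the look = 22/*u* + 4.2.

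| Assumed placebo uptake | Placebo patients needed | Enrolled at the look (of 44) |
|---|---|---|
| 100% | 11 | 22.0 + 4.2 = about 26 |
| 75% | 14.7 | 29.3 + 4.2 = about 34 |
| 60% | 18.3 | 36.7 + 4.2 = about 41 |
| 55% | 20 | 40.0 + 4.2 = 44.2, enrolment complete |
| 50% | 22 | enrolment complete |

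At 50% uptake the expected number of placebo biopsies is exactly 11, and the chance of never reaching 11 is 1 - P(Bin(22, 0.5) >= 11) = 1 - 0.584 = 42%.

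**Step 4. Break-even uptake.** The look falls after full enrolment when 22/*u* + lag >= 44.
- 10-week lag: *u* = 22 / (44 - 4.2) = 55%.
- 13-week lag (22 x 13/52 = 5.5 patients): *u* = 22 / (44 - 5.5) = 57%.
- With 10% drop-out, divide by 0.9: about 61% and 64%.

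**The case against.** **The triggers can nearly be reconciled by reading.** The count of 22 is the same in both. Section 10 says only that investigators will plan an initial evaluation at 50% accrual, and Section 7 could be read as stating what data that evaluation needs. This narrows the practical gap to about 10 weeks. It does not remove it, because Section 10 never says that follow-up must be complete.

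**The word for biopsied may simply mean past the 10-week visit.** The protocol uses biopsy as a label for that visit: Section 8.2.1 does so for the 10-week IPSS score, and the placebo row of the schedule does so for the end of tablet-taking. On that reading, optional tissue sampling delays nothing. The reading is reasonable, and it is why the uptake problem is stated only for the literal text.

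**A reader might infer that the look will come after enrolment is complete.** The documents do not support that. They give no uptake figure, and what they do say (standard care, a visit and biopsy for all subjects, recommended even in the placebo row) points to high uptake. At 60% uptake without drop-out the look still comes at about 41 of 44.

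**A reader might also infer that the stopping rule then protects nobody.** That goes too far. Section 10 carries the toxicity rules without any biopsy condition. Section 9 provides for adverse events at each visit, stopping of the study pill at Grade 3 or higher, and reporting to the IRB and FDA. Section 10 adds an annual committee review. What a late look would mainly delay is the comparison of biopsy results.

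**Conclusion.** The inconsistency is in the current text and needs no assumption about uptake: one look, one set of stopping rules, two triggers. Under uniform accrual the triggers are about 10 weeks or 4 patients apart, and the Section 10 trigger leaves about 18 of 22 patients with 10-week data.

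The further delay is conditional. It requires the literal reading of Section 7 and incomplete placebo biopsy uptake, which the documents neither state nor suggest is low. With near-complete uptake and no drop-out the look comes at about 26 of 44, leaving about 18 patients still to enrol. It follows full enrolment only at an uptake of about 55-57% or lower, or about 61-64% with the plan's drop-out rate.

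Underneath the timing question, the schedule sets a different biopsy requirement for each arm, against the text of Sections 5 and 7. That affects the comparison made at the look, as well as its date.

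**What to change.** 1. State one trigger, in the same words, in Sections 7 and 10: the look is held when the first 22 randomised patients have reached or missed the 10-week visit, whether or not a biopsy was done. This needs no uptake assumption, and drop-outs cannot hold it up.
2. Reconcile the biopsy wording in the Section 5 text, the Section 5 schedule and Section 7, so that disease status at the look is ascertained on the same basis in both arms. Which biopsy requirement applies is for the sponsor and investigators to decide. Changing the trigger alone would leave ascertainment unequal.
3. State whether enrolment continues or pauses while the 22nd patient completes follow-up.

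**Cost.** Items 1 and 3 are protocol wording and add no visits or procedures; whether item 2 adds any depends on how the wording is reconciled. The look comes about 10 weeks later than 50% accrual, with about 4 more patients enrolled unless there is a pause. It may include fewer than 22 biopsies, and the first 22 randomised may not split exactly 11 and 11.
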